## 2.7 Sample Size

Assuming a 25% attrition rate and allowing for 100 additional patients (10 per variable) in the multivariate analysis, for a treatment group ratio of 2:1:1 for adalimumab, traditional systemic agents and topical agents a total of 660 (330:165:165) patients will be required for 80% power and two tailed 5% significance. In addition, this sample size will be sufficient to detect a 20% (Relative Risk = 0.80) relative reduction in PGA between adalimumab and traditional systemic agents, and a similar difference between systemic and topical agents.

### 2.8 Patient Selection

Patients will be enrolled from the offices of community rheumatologists across Canada treating patients with PS. The sample of physicians invited to participate in the study will be selected in a way that it is a random representative sample of the Canadian population and distribution of dermatologists.

All patients with PS treated at the participating centers will be potentially eligible to be included in the study. Those fulfilling the study inclusion and exclusion criteria will be invited to participate in the study by the site investigator or designee. Treatment will be according to the treating physician's judgment and routine care and must adhere to the product monograph and regional regulatory requirements. Use of medications for the management of PS that is off – label or not in accordance with existing regulations will not be permitted. Prior to inclusion in the study all patients will be required to sign a written informed consent agreeing to allow use of their data in the study. Since this is not an interventional study and patients are treated as per routine care the purpose of the informed consent will be to allow the use of the data and contact of the patients by the study personnel as required. The study protocol, informed consent, questionnaires and participating physicians will be approved by a central or local independent ethics review board as required by regional or institutional regulations.

COMPLETE - PS Statistical Analysis Plan Version 3.0 July 23rd, 2015 Page 18 of 231

#### 2.8.1 Inclusion Criteria

The following inclusion criteria will be applied:

- 1. Adult >18 years old
- 2. Has provided written informed consent allowing the use of their data for the study and providing permission for contact by the study personnel.
- 3. Active moderate or severe Plaque PS according to the judgment of the treating physician.
- 4. The treating physician has decided to change the current treatment or add additional treatments for any reasons including but not limited to inadequate response, intolerance, sub-optimal compliance or patient preference.

#### 2.8.2 Exclusion Criteria

The following exclusion criteria will be applied:

- 1. Currently participating in another prospective study with similar objectives.
- 2. Patient cannot or will not sign informed consent.
- 3. Presence of other condition that, in the opinion of the treating physician, prohibits the patient from participating in the study or obscures the assessment of the treatment of Plaque PS.

#### 2.9 Treatment

In the current study patients will be treated with topical agents, traditional systemic agents and adalimumab as monotherapy or in combination. As an observational study all treatments will be accessed as per routine customary practice in the region. More specifically, ABBOTT will not supply or reimburse for any treatment used by the patients in the study. Patients will be prescribed the medications by the treating physician and will acquire these through the available insurance plan / government reimbursement or purchase

COMPLETE - PS Statistical Analysis Plan Version 3.0 July 23rd, 2015 Page 19 of 231

with their own funds. All medications will be used in accordance to the current marketing label, the product monograph and regional requirements.

Changing the patient's treatment including initiation of treatment with adalimumab must be exclusively the treating physician's decision and must be reached prior to patient screening and enrollment and has to be entirely independent of the conduct of the study. The observational nature of the study dictates that all treatments used in the current study, including adalimumab, must be prescribed as per routine care and in accordance to the Canadian and provincial marketing authorization and criteria.

#### 2.10 Outcome Measures

The following sections describe the outcome measures used to address the study objectives.

### 2.10.1 Efficacy Measures

### 2.10.1.1 Primary Endpoints

The primary effectiveness outcome measure of the current study will be the physician global assessment (PGA) of "0" or "1" indicating clear or minimal disease according to the following classification:

Score	Category	Description
	Clear	Plaque elevation = 0 (no elevation over normal skin)
0		Scaling = 0 (no scale)
0		Erythema = ± (hyper pigmentation, pigmented macules, diffuse
		faint pink or red coloration)
		Plaque elevation = ± (possible but difficult to ascertain whether
1	Minimal	there is a slight elevation above normal skin)
1		Scaling = ± (surface dryness with some white coloration)
		Erythema = up to moderate (up to definite red coloration)
	Mild	Plaque elevation = slight (slight but definite elevation, typically
2		edges are indistinct or sloped)
2		Scaling = fine (fine scale partially or mostly covering lesions)
		Erythema = up to moderate (up to definite red coloration)

## COMPLETE - PS Statistical Analysis Plan Version 3.0 July 23rd, 2015 Page 20 of 231

			Plaque elevation = moderate (moderate elevation with rough or
	3	Moderate	sloped edges)
			Scaling = coarser (coarse scale covering most of all of the lesions)
			Erythema = moderate (definite red coloration)
		Severe	Plaque elevation = marked (marked elevation typically with hard or
			sharp edges)
	4		Scaling = coarse (coarse, non tenacious scale predominates
			covering most or all of the lesions)
			Erythema = severe (very bright red coloration)
	5	Very severe	Plaque elevation = very marked (very marked elevation typically with hard sharp edges)
			Scaling = very coarse (coarse, thick tenacious scale over most of all
			of the lesions; rough surface)
			Erythema = very severe (extreme red coloration; dusky to deep red coloration)

The primary outcome measure will be the percent of patients with PGA score of  $\leq 1.0$  at 6 months of treatment.

### 2.10.1.2 Secondary Endpoints

The following secondary endpoints will be assessed:

- i. Time to achieving PGA  $\leq 1.0$  over 24 months of follow up.
- ii. Percent of patients with PGA  $\leq$  1.0 at 3, 12, 18 and 24 months.
- iii. Signs and symptoms suggesting onset of PsA:
  - Change in the modified Psoriasis and Arthritis Screening Questionnaire (PASQ). This is an 11 item tool that ascertains self-reported presence of joint pain and swelling. This will be assessed at 3, 6, 12, 18 and 24 months.
- iv. Change in Body Surface Area (BSA) of PS involvement at 6, 12, 18 and 24 months. The BSA is an indicator of disease severity and the affected area is expressed as a percentage of the total body surface area.

## COMPLETE - PS Statistical Analysis Plan Version 3.0 July 23rd, 2015 Page 21 of 231

- v. Change in Patient Global Assessment of Disease Activity based on a six point Likert Scale at 3, 6, 12, 18 and 24 months.
- vi. Change in the Dermatology Quality of Life Index (DLQI) at 3, 6, 12, 18 and 24 months. The DLQI is a self-administered questionnaire comprised of 10 items assessing a patient's skin and problems associated with skin disease. The 10 questions in the DLQI converge into six domains that measure symptoms and feelings, daily activities, leisure, work and / or school, personal relationships and satisfaction with treatment.
  - Proportion of patients achieving and time to DLQI ≤ 1 through the 24 months of treatment.
- vii. Change in Beck Depression Inventory at 6, 12 and 24 months: This will be used to assess the presence and severity of depression. It consists of 21 items converging to two scales measuring somatic and affective components of depression. The questions assess hopelessness and irritability, cognition such as guilt or feelings of being punished, as well as physical symptoms such as fatigue, weight loss and loss of interest in sex. Given the important emotional and social impact of psoriasis assessing psychological impairment is important in order to fully appreciate the impact of the disease and effect of treatment on the patient's life.
- viii. Change in Medical Outcome Study Short Form 12 (SF-12) at 6, 12 and 24 months. The SF-12 Health is a 12-item general health self-administered questionnaire consisting of 8 scales measuring physical function, physical role limitations, vitality, general health, pain, social function, emotional role limitations, and mental health.
  - ix. Change in Working Limitations Questionnaire (WLQ) at 6, 12 and 24 months. The WLQ is a self-administered questionnaire comprised of 25 questions. It assesses the degree to which the patient's work is affected due to health problems or health-related

COMPLETE - PS Statistical Analysis Plan Version 3.0 July 23rd, 2015 Page 22 of 231

productivity loss. The 25 questions are further divided into four scales: time management, physical demands, mental-interpersonal demands and output demands. The scoring for the WLQ ranges from 0 (none of the time) to 100 (all of the time) and represent the portion of time in the prior two weeks that those answering the questionnaire were limited in their abilities while at work. Furthermore, an algorithm, is present that can convert scores obtained using the WLQ into an estimate of productivity loss. Considering the important effect of PS on the patient's ability to deal with the emotional and physical demands of employment, the assessment of the impact of disease and treatment on work related productivity loss is highly relevant.

- x. Health Care Utilization and Health Economics Questionnaire through the 24 months of treatment. This will be a descriptive self-administered series of questions aimed at measuring the patient's health care utilization and economic impact of the disease. More specifically the questionnaire will ascertain the frequency of physician visits, utilization of other health care professionals, visits to clinics, emergency rooms and hospitalizations that related to PS. In addition, use of prescription and non-prescription medications for the management of PS will be determined. Out of packet expenses for medications and health care will be assessed. The patient's occupation and household income range will be used as proxy to socioeconomic status.
- xi. Compliance with treatment will be assessed through the 24 months of treatment by self report of missed topical applications, medication doses or adalimumab injections.
- xii. Change in medical history and concomitant medication use through the 24 months of treatment will be recorded assessed by the treating physician as per routine care.
- xiii. Change in use and frequency of phototherapy for PS though the 24 months of treatment will be ascertained by a targeted question in the patient assessment.

COMPLETE - PS Statistical Analysis Plan Version 3.0 July 23rd, 2015 Page 23 of 231

### 2.10.2 Safety Measures

Safety and tolerability will be assessed with the incidence of treatment-emergent adverse events. Incidence of treatment emergent serious adverse events will be recorded by the treating physician through the 24 months of treatment. Severity of the adverse event and causal relation to the treatment will be assessed by the treating physician. All adverse events will be coded as per the MedDRA dictionary of terms.

i. All serious adverse events will be recorded and reported as per regional regulatory guidelines and requirements.

## 3 Statistical Methods

## 3.1 Statistical Handling Policy

### 3.1.1 Analysis Conventions

This section details general guidelines to be used for the statistical analyses. Deviations from these general policies may be given in the specific detailed sections of this statistical analysis plan. When this situation occurs, the rules set forth in the specific section take precedence over the general conventions. The following policies will be applied to all data presentations and analyses:

- Two-tailed tests will be performed for all analyses that use statistical testing with a significance level of  $\alpha = 0.05$ .
- All p-values will be rounded to 3 decimal places. All p-values that round to 0.000 will be presented as '<0.001' and p-values that round to 1.000 will be presented as '>0.999'. Any p-value  $\leq$ 0.05 will be considered statistically significant.
- Summary statistics will consist of the number and percentage of responses in each category for discrete variables, and the mean, median, standard deviation (SD), minimum, maximum, and 95% confidence interval for continuous variables.

COMPLETE - PS Statistical Analysis Plan Version 3.0 July 23rd, 2015 Page 24 of 231

- All mean and median values will be formatted to one decimal place. Standard deviation values will be formatted to two decimal places.
- All percentages will be rounded to one decimal place. Where appropriate, the number and percentage of responses will be presented in the form XX (XX.X %), where the percentage is in the parentheses.
- All listings will be sorted for presentation in order of treatment group, site number, subject number, and date of procedure or event.
- When necessary for analysis purposes, partial dates will be completed (i.e., turned into complete dates) using the most conservative approach. Where appropriate, all analysis and summary tables will have the population sample size for each treatment group in the column heading.
- All analyses and summary tables will have the population sample size for each treatment group in the column heading.
- Tables will include footnotes describing the analyses involved, and listings of covariates included in the analyses, where relevant.
- In order to maintain vertical alignment, all tables and listings will be incorporated into MS Word and an 8 point Courier New font will be used. For practical reasons, the point size may be reduced to (but not less than) 7 point for tables/listings that contain too much information to fit into a single page.
- Version 9.2 (or later) of SAS® will be the statistical software package used to produce all summaries, listings, statistical analyses, and graphs.
- Version 12.1 (or higher) of MedDRA will be used for adverse event and pre-treatment conditions coding.

COMPLETE - PS Statistical Analysis Plan Version 3.0 July 23rd, 2015 Page 25 of 231

• Version 2009 (or later) of the World Health Organization (WHO) Drug Classifications will be used for the coding of medications.

### 3.2 Bias by Indication

One of the most important challenges in conducting between treatment comparisons in observational or naturally occurring experiment studies is confounding by indication. This occurs because the patients are allocated to different treatment groups not randomly but on the basis of the treating physician's judgment. This may result in an imbalance of the prognostic profile between the treatment groups and therefore confounding in the assessment of differences with respect to the study outcome measures. Multi-variable models that include potential confounders as covariates or propensity scores developed with potential confounders are valid solutions for the statistical adjustment of between group baseline differences and minimization of bias. The development of the propensity score will be based on categorical or multinomial logistic regression and binary logistic regression for the assessment of the profile differences between patients treated with adalimumab, topical agents and traditional systemic agents. Stratification of the analyses into homogeneous subgroups is another solution. All of these solutions will be explored in the current study. Unfortunately determination of the appropriate approach is data driven and cannot be determined a-priori.

## 3.3 Unequal Time Periods for Assessments

Another problem with observational naturally occurring experiments is that patient assessments are not dictated by a strict protocol but as per the real – life setting they are based on routine clinical practice, the judgment of the physician and the availability of the patient. These create a problem with unequal duration of treatment and follow up and when assessments at defined time intervals are required. The mixed effects repeated measures

COMPLETE - PS Statistical Analysis Plan Version 3.0 July 23rd, 2015 Page 26 of 231

models that will be used in the current study resolve this issue. With these models the least square mean will be used to estimate the value of the variable at specific time points.

3.4 Missing Data

One more, although less unique, problem with observational studies is missing data. This is particularly problematic with self-administered questionnaires where capture of the missing data is not possible. The mixed effects models described earlier compensate for missing data points in individual visits. For clinical data all efforts will be made to retrieve any missing data point. For missing responses on questionnaire items the coding for the majority of the tools used in the current study provide imputation solutions for missing responses. Furthermore, in the current study in order to assess the likelihood of bias, the pattern of missing data will be evaluated to determine whether the data follow a missing at random pattern or whether there is a systematic non-random distribution of missing data.

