## 6.4 Study Duration

All patients will be followed for 24 months. Given the observational nature of the study there will be no pre-defined protocol driven assessments and physician visits could take place according to the routine practice or the judgment of the treating physician. However, assessments at 3, 6, 12, 18 and 24 months after baseline will be recommended and encouraged given that this is within the acceptable practice patterns for patients undergoing treatment for moderate to severe psoriasis. In certain cases patients may be assessed more frequently than what will be recommended. Physicians will be asked to record in the Case Report Forms data from all visits occurring during the study period.

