#### 10.3 Sample Size Calculations

Sample size considerations are based on the primary objectives of the study, specifically the proportion of patients that achieve a PGA rating of "0" or "1" at 24 months of follow up.

The following data and assumptions were used to determine the sample size requirements for the study:

- In the Champion study after 16 weeks of treatment 73% of the patients treated with adalimumab, 30% of the patients treated with methotrexate and 11.3% of the patients treated with placebo achieved PGA values of 0 or 1 indicating clear or minimal disease.
- The Champion study was a randomized placebo controlled clinical trial that was based on a strict protocol not allowing any concomitant treatment and enrolling a very well defined patient population. In the current study we can assume that we will observe similar trends in the order of treatment effectiveness, by which adalimumab will be superior to traditional systemic agents, which will be superior to topical agents. However, due to case mix and use of concomitant medications the actual therapeutic effect and difference between groups may be more variable and lower than that observed in the CHAMPION study. We can therefore assume that due to patient profile, and in order to be conservative, that the observed proportion of patient achieving and maintaining a PGA≤ 1 at 6 months will be approximately 50%. A relative reduction of 20% (RR = 0.80) in PGA would be considered as the minimum acceptable for clinical importance. Therefore, the current study we should be powered to detect a 20% relative reduction between adalimumab and traditional systemic agents, and a similar difference between systemic and topical agents. It follows that if we assume that the proportion of patients treated with adalimumab that achieve PGA ≤1.0 at six months will be

50%, the proportion in the patients treated with traditional systemic agents will be 40% ( $\underline{RR}$ =0.8) and that in patients treated with topical agents will be 32% ( $\underline{RR}$  = 0.8).

• For an expected treatment group ratio of 1:1 for adalimumab: traditional systemic agents and topical agents a total of 360 (180: 180) patients will be required for 80% power and two tailed significance of 5%. Assuming a 25% attrition rate and allowing for 100 additional patients (10 per variable) in the multivariate analysis 660 (330:165:165) patients will be recruited.

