## 3.10 Analysis of the Primary Objective

For the primary objective, between-group differences with respect to achieving a PGA of "0" or "1" at six months will be assessed with simple logistic regression analysis and multivariate logistic regression models adjusting for potential confounders or the propensity score. In addition, a Generalized Estimating Equation (GEE) model will be used to compare

COMPLETE - PS Statistical Analysis Plan Version 3.0 July 23rd, 2015 Page 30 of 231

the three patient groups in terms of achieving a PGA of "0" or "1" over 24 months of treatment. Kaplan Meier based time to event (survival) analysis will be used with the log-rank test to assess the statistical significance of the between group differences. Cox's proportional hazards model will also be used to adjust for potential confounders or the propensity score.

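### SAP 3.4 asks the pattern of missing data to settle whether data are missing at random; observed data cannot settle it, and no missing-not-at-random sensitivity analysis is planned

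*SAP*

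**What the plan says.** SAP 3.4 gives the handling of missing data in one paragraph. Missing visits are left to the models: "The mixed effects models described earlier compensate for missing data points in individual visits". Missing clinical data are to be chased, and missing questionnaire items follow each tool's own imputation rules. Then, "in order to assess the likelihood of bias", the plan adds that "the pattern of missing data will be evaluated to determine whether the data follow a missing at random pattern" or instead show a systematic, non-random distribution. No test, decision rule or consequence is attached to either finding.

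SAP 3.6 adds visit completion and discontinuations by treatment group, the reasons for discontinuation, and a time-to-discontinuation analysis.

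The primary comparison in SAP 3.10 is not a mixed model. PGA 0/1 "at six months will be assessed with simple logistic regression analysis", with adjusted logistic models alongside. In addition, "a Generalized Estimating Equation (GEE) model will be used to compare" the cohorts over 24 months. The mixed models belong to the continuous secondary changes in SAP 3.11.

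Protocol 6.4 states that "All patients will be followed for 24 months" but also that "there will be no pre-defined protocol driven assessments", so visits follow routine practice. Protocol 10.3 sizes the study "Assuming a 25% attrition rate".

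**The concern.** Missing at random means that, given what was observed, the chance of being missing does not depend on the value that was not seen. Missing not at random means that it does. The two differ only in a feature of the unseen values, so no inspection of observed data can separate them. A pattern analysis can show that missingness depends on observed variables. If missing at random is read loosely as missing completely at random, observed data can refute that, but still cannot confirm it.

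The sentence therefore gives the check a task it cannot perform, and the task is the one that matters: judging whether bias is likely. A clean pattern would carry no information on the point, and nothing else in the plan supplies it.

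The setting makes the question a live one. Treatment is not randomised, visits are not fixed, and the retention paragraph in Protocol 6.5.1 names loss to follow-up among the study's main challenges. The reasons for an absent assessment could differ between cohorts.

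**Working it through.** The plan gives no figure to reproduce; the point is what observed data can identify. The arithmetic shows how far identical observed data can diverge in meaning.

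**Inputs**
- Observed month-6 response: 50% adalimumab, 40% traditional systemic. These are the planning rates in Protocol 10.3, used here as if observed.
- Missing fraction *m*: 25% in each cohort at month 6. This is an assumption. Protocol 10.3 gives one overall attrition rate, not tied to a cohort or to month 6. The range shown is 10% to 35%.
- Response among missing patients, *qA* (adalimumab) and *qS* (systemic): unknown by definition, so varied.

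**Formula**

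Full-cohort rate = (1 - *m*) × observed rate + *m* × *q*, so

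difference = (1 - *m*) × 10 points + *m* × (*qA* - *qS*).

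**Results at *m* = 25%, with the same observed data in every row**

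| *qA* | *qS* | Adalimumab | Systemic | Difference |
|---|---|---|---|---|
| 50% | 40% | 37.5 + 12.5 = 50% | 30 + 10 = 40% | +10 |
| 30% | 40% | 37.5 + 7.5 = 45% | 30 + 10 = 40% | +5 |
| 50% | 20% | 37.5 + 12.5 = 50% | 30 + 5 = 35% | +15 |
| 30% | 60% | 37.5 + 7.5 = 45% | 30 + 15 = 45% | 0 |
| 0% | 100% | 37.5 + 0 = 37.5% | 30 + 25 = 55% | -17.5 |
| 100% | 0% | 37.5 + 25 = 62.5% | 30 + 0 = 30% | +32.5 |

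**Bounds at other missing fractions**
- 10%: 45 - (36 + 10) = -1.0 to (45 + 10) - 36 = +19.0 points.
- 35%: 32.5 - (26 + 35) = -28.5 to (32.5 + 35) - 26 = +41.5 points.

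The difference vanishes when *qA* is below *qS* by (1 - *m*) × 10 / *m* points: 90 points at 10% missing, 30 at 25%, and about 18.6 at 35%.

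**Simulation of the check.** Two mechanisms were built to give the same observed-data distribution, each with 330 v 165 patients and 2,000 datasets. The check was a logistic regression of missingness on cohort and one baseline covariate, tested at 5%.
- Missing at random, true difference 10 points: the check flagged 5.1% of datasets, and the complete-case test was significant in 44.7%.
- Missing not at random, both cohorts truly 45% (missing patients responding at 30% v 60%): the check flagged 5.2%, and the complete-case test was significant in 45.1%.

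The check behaves alike in both cases, although in the second every significant result is false. The covariate was unrelated to outcome and the second mechanism is a strong one. The simulation shows the principle, not the error rate to expect in this study.

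**The case against.** **The SAP does not say that a clean pattern will be reported as proof.** This stands. No action follows from the check, so a reader who infers that the plan would formally clear a biased comparison goes beyond the text. The sentence still promises a determination that cannot be made.

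**The pattern check is not the only information on dropout.** This also stands. The SAP 3.6 tables bear on differential dropout, and a check using month-3 PGA and reasons for discontinuation would be richer than the one simulated. All of this is observed information. It can reveal associations but does not identify dependence on the unseen PGA.

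**The 25% is stretched.** It is overall attrition over a 24-month study, so month-6 missingness could be lower. Protocol 6.5.1 also keeps patients who stop or switch treatment in follow-up, and does not make poor response or adverse events grounds for withdrawal. That weakens the link between outcome and missingness without removing it. At 10% missing the lower bound is only -1.0 points, and removing the difference would take a 90-point gap among missing patients.

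**The remedy exceeds the defect.** Rewording alone would cure the false claim. But it would leave the stated aim, assessing the likelihood of bias, with no method behind it.

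Two stronger readings are tempting. One is that the data could support conclusions on either side of a relative-risk threshold of 0.80. In Protocol 10.3 that ratio is the minimum effect of clinical importance used for sample size; SAP 3.1.1 and 3.10 draw conclusions from two-sided 5% tests. The other is that these figures show the mixed models to be biased. They concern month-6 PGA, which is analysed by logistic regression; no size has been worked out for the mixed-model endpoints.

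**Conclusion.** The point holds as one of method: SAP 3.4 states a check that cannot deliver its stated purpose, and the supplied text contains no missing-not-at-random sensitivity analysis to stand in for it. The discontinuation summaries in SAP 3.6 are useful but descriptive.

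Under the 25%-per-cohort assumption, one set of observed data is compatible with a true difference of 10, 5, 15 or 0 points. How much this matters depends heavily on month-6 missingness by cohort, which the documents do not give.

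The conclusion that the check cannot separate the mechanisms needs none of these numbers. What is not shown is that missingness here depends on outcome, that the comparison is biased, or that any planned decision turns on the check. The change is worth making before analysis but does not by itself invalidate the plan.

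**What to change.** Replace the final sentence of SAP 3.4 with text to this effect:

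> Missingness will be described by cohort, visit, baseline values and prior PGA. Missing at random is an assumption that the data cannot verify. For the primary month-6 PGA 0/1 comparison, the response rate assumed for patients with missing PGA will be varied separately by cohort, and the report will show where the two-sided 5% conclusion changes.

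The SAP should also name the imputation method and the grid of assumed rates before the data are analysed, and say that the sensitivity analysis covers adalimumab against each comparator cohort. A delta-adjusted version for DLQI change from the mixed model is optional.

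The cost is SAP wording, modest extra programming and one or two extra tables. No new data are needed.
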